A Phase II Randomized Trial to Assess the Effectiveness and Safety of the ID-Cap System for Medication Ingestion Monitoring and Enhancing Adherence

In pharmacotherapy trials involving drug-dependent individuals, medication compliance is a significant issue, as rates tend to be low and adherence to medication may predict improved outcomes (Baros et al, 2007; McRae et al, 2004; O'Brien et al, 1996; Somoza et al., 2010). However, methods commonly used to determine compliance may result in inaccurate measurement of adherence. For example, in a pharmacotherapy trial for cocaine dependence, a comparison of an electronic medication event measurement system (MEMS), self-report, and a biochemical tracer (riboflavin) found that MEMS-based estimates of compliance were substantially lower (28%) than self-report (87%) or riboflavin (78%) (Mooney et al, 2004). Although MEMS are widely regarded as the gold standard measure of patient compliance, a critical shortcoming of this approach is that actual medication ingestion is not measured; rather, the system is limited to registering times when the closure is opened and when it is closed. Further, the MEMS is not able to transmit real-time compliance data to a clinical site and as such there is limited opportunity to intervene if non-compliance is suspected. It is therefore essential to develop measurement systems that not only accurately and objectively measure compliance, but can also have the potential to increase compliance in difficult to treat disorders such as addiction. To achieve this aim, we propose to assess the effectiveness and safety of the ID-Cap-M, a novel compliance measurement device, in a healthy population. Forty healthy individuals will be recruited and randomized into one of two intervention groups: (1) a group receiving a standard capsule containing 50mg of riboflavin to be ingested once daily and dispensed with a MEMS 6 TrackCap (n=20), and (2) a group receiving an ID-Cap-M containing 50mg of riboflavin to be ingested once daily in which participants are contacted and compliance encouraged if the ID-Cap is not ingested as directed (n=20). Specific aims and corresponding hypotheses of this clinical investigation include:

Aim 1: To assess the effectiveness of the ID-Cap-M system for medication ingestion monitoring and enhancing medication adherence.

Hypothesis 1a: The ID-Cap-M system will detect over 95% of medication ingestion events as ascertained by doses of medication recorded by the ID-Cap System that are taken as prescribed (once daily and on time with use of ID-Cap System as instructed) over those scheduled.

Hypothesis 1b: The ID-Cap-M system will have an advantage over the MEMS caps on monitoring and enhancing medication adherence expressed by a proportion of daily medication doses reported by the system to be ingested (ID-Cap System) or accessed (MEMS Caps) as prescribed (defined as within the scheduled administration time) over the study period.

Exploratory Aim 2: To assess the safety of the ID-Cap-M system when used in a healthy population by documenting the frequency and severity of adverse events.

Exploratory Hypothesis 2: Participants randomized to receive the ID-Cap-M system will report similar rates of adverse events as participants randomized to receive standard capsules.

Overview: The primary objective of the clinical trial is to evaluate the acceptability, tolerability, and efficacy of the ID-Cap-M in a healthy population. The primary outcome will be medication compliance as measured by the proportion of days adherent to taking medication over a four week period.

Subjects: 40 participants between the ages of 18 and 65 will be recruited over a 10-month period. Additional inclusion criteria include ability to provide informed consent, functioning at an intellectual

Program Director/Principal Investigator (Last, First, Middle): [name]

level sufficient to allow accurate completion of assessments, and having a Body Mass Index (BMI) below 35. Exclusion criteria include women who are pregnant, nursing or of childbearing potential and not practicing an effective means of birth control; subjects with evidence of a significant medical condition which may affect capsule passage (including but not limited to acute gastroenteritis, Crohn's disease, small bowel tumors, intestinal adhesions, ulcerations, and radiation enteritis); subjects with a history of hypersensitivity to riboflavin or any other capsule component; subjects with embedded electronic devices; subjects with a current major psychiatric disorder as these may interfere with assessment measures; subjects meeting DSM-V criteria for moderate to severe substance dependence (other than nicotine or caffeine) within the past 60 days; and subjects who, in the investigator's opinion, would be unable to comply with study procedures or assessments, or would be unacceptable study candidates (e.g., poses threat to staff).

Recruitment: Subjects will be primarily recruited through media and internet advertisements. "Respondent-Driven Sampling" (RDS), will also be used to enhance recruitment of the sample (Heckathorn, 1997). The RDS sampling methodology is based on recruiting the eligible friends and acquaintances of each participant so that the sample "snowballs". Each eligible participant who completes an interview will be given coupons to pass on to other potential participants. The coupons will have a unique code linked to the person who passes them out. A referral will be instructed to call the site offices for screening and, if eligible, an appointment for further evaluation. If a referral completes the screening process and is eligible for the study, the participant who referred the person can redeem the coupon for \$20. We have an active recruitment network, and have consistently surpassed recruitment goals with studies in this population.

Screening/Assessment: A quick screen will be used to initially determine study eligibility. This questionnaire is focused on inclusion/exclusion of psychiatric diagnoses, medical status, and ability and willingness to complete study procedures. Potential subjects will be given a full description of the study procedures and asked to read and sign an IRB-approved Informed Consent Form if interested in participating. Appropriate modules of the Mini-International Neuropsychiatric Interview (M.I.N.I.) will be used to assess exclusionary psychiatric diagnoses (Sheehan et al, 1998). A general medical history and physical exam will also be performed to ensure that the subject is eligible to participate. Urine drug screens will be performed at the screening visit in order to rule out substance abuse. For female participants, a urine pregnancy test will be completed prior to urine drug screening.

Group Assignment/Intervention: After inclusion into the study, participants will be randomized into one of two intervention groups. Group 1 (n=20) will receive a standard capsule containing 50mg of riboflavin to be ingested once daily and dispensed with a MEMS 6 TrackCap. Group 2 (n=20) will receive an ID-CAP-M containing 50mg of riboflavin to be ingested once daily. Their compliance will be measured by data collected by an e-Tect reader worn around the neck on a lanyard. Participants randomized to this group will also receive reminder calls and/or text messages to ingest the study medication if a signal is not sent from the e-Tect reader to the study team within one hour of the end of the scheduled medication administration time window. In the event that a daily pill detection is not obtained for a subject in Group 2, but they report taking the pill as directed, they will be asked to come in to the clinic to provide a urine sample for riboflavin assessment. Group 2 participants will be provided with a loaner smartphone for e-Tect application download if they do not own a personal one or do not wish to use their own. The smartphones will be activated by a data plan, and will be of no cost to the participants. All applications of the phone will be disabled with the exception of the e-Tect

Program Director/Principal Investigator (Last, First, Middle): [name]

software needed to transfer data. Providing the necessary technology will prevent the exclusion of individuals without smartphone access or those who cannot afford to pay for a smartphone data plan. Group 2 will also provide biometric data for compliance measurement, specifically ECG. These measurements will be collected by their eTect reader.

Study visits: The study duration will be approximately six weeks. At the initial randomization visit, participants will be trained on use of the devices (MEMS 6 TrackCap for Group 1 and biometric data collection/ID-Cap-M for Group 2) and medication administration will be observed. A 30-day supply of study capsules will be dispensed. Participants will be instructed to take each dose by 12PM daily. Participants will return to the clinic approximately five weeks (within one week following last dose) after their initial randomization for an End of Study (EOS) visit to discuss overall medication compliance and return their study equipment (pill bottles, unused capsules if any, and MEMS 6 TrackCap or ID Cap Reader). For those in Group 2, passage of ID-Caps will be confirmed at this visit via abdominal x-ray.

Safety Assessment: Adverse events (AEs) will be assessed at the End of Study visit. The research clinician will identify potential adverse events by asking the subject a question such as: "Have you had any problems or side effects since we saw you last (such as flu, headache, nausea, or other problems)?" The type of AE, severity of AE, and relationship to the study intervention will be recorded. At their initial randomization visit, subjects will be given detailed information regarding clinic contact procedures during and afterhours should this be necessary during their study participation. An abdominal X-ray will also be completed at study completion to verify passage of the capsules from the gastrointestinal tract for those in Group 2.

Follow-up Plan: In the event that an adverse event occurs during the study, a subject will be followed to resolution. Participants will be provided incentive compensation to attend the EOS visit and return the MEMS 6 TrackCap or e-Tect reader and cell phone (if one was provided).

Compensation: Subjects will be compensated \$30 for screening, (\$20 for interview, \$10 for H&P). They will be compensated \$250 for the End of Study visit (\$100 for attendance and \$150 for return of their MEMS 6 TrackCap or ID Cap Reader). If a Group 2 subject did not return for an unscheduled urine sample as requested during the study, they will receive \$50 for attending the EOS visit (versus \$100).

Data Management and Reduction: All paper-based assessments (other than laboratory reports) will be entered into REDCap, a secure, web-based application designed exclusively to support data capture for research studies. REDCap provides an intuitive interface for data entry (with data validation), audit trails for tracking data manipulation, and automated export procedures for data downloading to statistical packages such as SPSS and SAS. Completed assessments will be entered within two weeks after the information has been collected from the subject. Quarterly database management and data integrity audits will be conducted and reports submitted.

Statistical Methods: Univariate descriptive statistics and frequency distributions will be calculated for all variables. Departures from distributional assumptions for the proposed parametric methods will be identified and appropriate transformations of the data will be applied or alternative procedures (semi/non parametric methods) will be employed. Values for demographic, clinical, and other prognostic variables will be compared for imbalance across treatment groups. ***Aim 1:*** The hypothesis

Program Director/Principal Investigator (Last, First, Middle): [name]

that the ID-Cap-M will improve compliance will be tested by comparing the number of medication adherent days (defined as ingestion of dose of medication within one hour of scheduled time) in the group receiving the ID-Cap-M with the group using a MEMS 6 TrackCap. The primary analysis of the difference in the number of adherent days will be done using a two group ANOVA model. Additional model analysis will be conducted assuming a binary pattern of responses on each day and fit into a Generalized Linear Model using a Generalized Estimating Equations (GEE) framework. **Exploratory Aim 2:** To test the safety and tolerability of ingestion of the ID-Cap-M versus standard capsules, the number of adverse event reported in the 20 subjects taking the ID-Cap will be compared to the number of events in the 20 subjects assigned to standard capsules. Analysis will be performed using a Pearson Chi-Square test statistic.

Other Statistical Considerations: The primary method of analysis will be through the use of the intent to treat sample where missing compliance data will be deemed non-adherent. However, other methods of missing data analysis will be employed and a sensitivity analysis of the various methods will be presented.

Sample Size Justification: The proposed study intends to evaluate the feasibility of inclusion of ID-Caps to monitor compliance in medication trials involving substance abusing subjects. The current study is a 30-day efficacy evaluation of the ID-Cap-M versus MEMS 6 TrackCap. **Aim 1:** With 20 subjects receiving the active ID-Caps and 20 receiving MEMS 6 TrackCap, we will have 80% power with a two sided $\alpha=0.05$ to detect an effect size of 0.95 (Cohen's *d*), which is equivalent to a difference of 0.95 adherent days between the two study groups for each unit in the standard deviation (example: with a SD of 10 days, we will be able to detect a difference of 9.5 days between groups)..

Design Considerations: *Choice of study population.* The determination was made to conduct this initial tolerability and feasibility trial in healthy individuals. After establishment of safety and efficacy in this population, subsequent studies will be conducted in drug-dependent populations. *Use of riboflavin.* Riboflavin is a water-soluble vitamin; it has no psychoactive properties and is excreted in the urine. A dose of up to 150 mg riboflavin daily has been shown to be well-tolerated by patients and easily measurable in patients' urine at levels 10-fold greater than normal using chromatographic separation and flurometric detection (Anton, 1996). As riboflavin is commonly used as a compliance measure in medication studies (Dubbart et al, 1985; Del Boca et al, 2006), it was considered an appropriate comparison marker to include.

Timeline: As we have an active recruitment network and trained staff in place, we anticipate minimal time required for study start-up. Given our previous recruitment rates for non-treatment studies (7 participants/month) we anticipate completion of the clinical trial within 12 months.

HUMAN SUBJECTS RESEARCH

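### Hypothesis 1a's 95% detection target mixes sensor detection with adherence, and no interval or test is planned against it

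*Combined protocol and SAP*

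**What the plan says.** Hypothesis 1a, under Aim 1, says "The ID-Cap-M system will detect over 95% of medication ingestion events". It measures this by doses the system records that are "taken as prescribed (once daily and on time with use of ID-Cap System as instructed) over those scheduled".

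Only the ID-Cap arm contributes: "Group 2 (n=20) will receive an ID-CAP-M containing 50mg of riboflavin to be ingested once daily". The number of scheduled doses per person is 30 if taken from Study visits ("A 30-day supply of study capsules will be dispensed"), or 28 if taken from the Overview's primary outcome ("the proportion of days adherent to taking medication over a four week period").

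Statistical Methods, Aim 1, covers the comparison of the two arms: "The primary analysis of the difference in the number of adherent days will be done using a two group ANOVA model". A further model treats each day as a binary response, "fit into a Generalized Linear Model using a Generalized Estimating Equations (GEE) framework". Descriptive statistics are promised for all variables. Sample Size Justification addresses only the between-arm difference. Neither section mentions the 95% figure, a one-sample test, a confidence interval or a success rule for 1a.

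**The concern.** There are two linked problems.

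**The ratio does not measure what the hypothesis claims.** The claim is about detecting ingestions, but the denominator is doses scheduled. The ratio is the product of two quantities: the share of scheduled doses taken as prescribed, and the share of those that the system records. A perfect sensor fails if participants skip doses. A late dose that the sensor does record also counts against it. If the rule in Other Statistical Considerations that missing data count as non-adherent is carried over to 1a, lost data are added to the same total.

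**The target has no error control.** A figure of 95% invites a yes-or-no conclusion, but the plan does not say how uncertainty enters it. All the doses come from 20 people, each with one reader, so failures to wear the reader or transmit data are likely to cluster by person.

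Detection is the device's central claim, and Design Considerations says that studies in drug-dependent populations follow once safety and efficacy are established here. A statement that detection exceeds 95% would be carried into that decision.

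**Working it through.** **1. The plan's own sample-size figure.** It states 20 per group, 80% power, two-sided α = 0.05 and d = 0.95. By the normal approximation, n per group = 2(1.960 + 0.842)²/0.95² = 17.4, so 18; with the t distribution it is 19. At n = 20 the t-test power is 83.3%, and 80% power is reached at d = 0.91. The statement is slightly conservative and sound, but it concerns the arm comparison only.

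**2. What the denominator does.** Scheduled doses number 20 × 30 = 600, or 20 × 28 = 560. Suppose the sensor is perfect. The ratio stops exceeding 95% once 30 of 600 doses are skipped or late (570/600 = 95.0%), or 28 of 560 (532/560 = 95.0%). That is an average of 1.5 or 1.4 doses per person over the whole study.

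**3. Comparing the observed proportion with 95%.** Exceeding 95% needs at least 571 of 600 or 533 of 560. If the true ratio is 95% and doses are independent, the exact binomial probability is 47.4% for 600 doses and 47.3% for 560. If the true ratio is 94%, it is 13% and 14%.

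**4. Allowing for clustering.** The documents give no ICC, so 0.02 to 0.20 is an assumption. Counts were simulated as beta-binomial for 20 people with 30 doses each. The design effect is 1 + 29 × ICC, and the effective number of doses is 600 divided by it. Three rules were compared:

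- A: observed proportion above 95%.
- B: exact binomial 97.5% lower limit above 95%, treating 600 doses as independent (needs at least 581/600 = 96.8%).
- C: lower limit of a participant-clustered two-sided 95% interval above 95%. On the logit scale the limit is logit(p) − t(0.975, 19 df) × SE, with SE = √V / [p(1 − p)] and V = (20/19)² Σ(xᵢ − 30p)²/600². Here xᵢ is person i's count and p is the pooled proportion.

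| ICC | Design effect | Effective doses | A, true 95% | B, true 95% | C, true 95% | C, true 98% | C, true 99% |
|---|---|---|---|---|---|---|---|
| 0.02 | 1.58 | 380 | 49% | 5% | 2% | 75% | 94% (95%) |
| 0.05 | 2.45 | 245 | 50% | 10% | 3% | 57% | 80% (83%) |
| 0.10 | 3.90 | 154 | 52% | 16% | 4% | 44% | 63% (70%) |
| 0.20 | 6.80 | 88 | 53% | 24% | 6% | 35% | 45% (61%) |

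The last column scores trials with every dose detected as failures, because the logit limit is undefined there. The figure in brackets scores them as successes. At a true 99% and ICC 0.20, about 16% of trials are of this kind.

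With 28 doses per person, rule A gives 49–53% over the same ICC range. If the true ratio is 94%, rule A is met in 19–37% of trials with 30 doses.

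**5. Reading the table.** Rule A passes about half the time at the threshold whatever the correlation. Rule B's nominal error is 2.5%, but it reaches 5–24%. Rule C stays at 2–6%, so it can still exceed 2.5% at higher correlation. A plain t limit on participant-level proportions did worse: 7–17% at ICC 0.05 to 0.30.

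**The case against.** **No success rule is written.** A reader might infer that the plan will declare 1a met whenever the observed proportion exceeds 95%. The documents do not say so. They state a hypothesis, and the half-the-time figure is conditional on the natural reading of it. Any roughly unbiased estimate exceeds its true value about half the time. This stands as a limit on the finding, but the absence of a rule is itself the gap.

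**The plan does not treat doses as independent.** A reader might infer that it does. It does not, and the GEE model named for Aim 1 accommodates within-person correlation and could yield an ID-Cap arm estimate with an interval. The plan does not assign it that job, and the comparison with 95% is not mentioned there.

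**A pill count is not ingestion.** Counting capsules dispensed minus returned treats lost or discarded capsules as swallowed, so it understates detection. The plan already has a dose-level check: under Group Assignment/Intervention, a participant who reports taking an undetected dose is asked for a urine riboflavin sample. This stands, and the two sources should be used together.

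**A logit limit is weakest where the device works best.** With every dose detected it is undefined, and with very few misses the robust variance rests on little information. This also stands, and a rule for that case has to be written down.

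**1a is not the primary outcome.** The primary outcome is the proportion of adherent days, and section 5.9 calls the trial preliminary. That limits the weight of the point but does not remove it, because the plan itself sets the numerical target.

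**Conclusion.** The concern holds as a secondary point. Hypothesis 1a words a detection claim but defines a ratio that combines detection with adherence, and the plan attaches no interval or test to its 95% bar. On the natural reading, a system truly at 95% would meet the bar about half the time: 47–53% with 20 people and 28 or 30 doses each, over ICC 0 to 0.20.

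The size rests on three assumptions: that the observed proportion alone is compared with 95%, that correlation is within the assumed range, and that counts are beta-binomial. The half-the-time result is insensitive to the last two. The chances of success under a clustered limit are not, and they were computed for 600 doses, not for the somewhat smaller number actually ingested.

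Two stronger readings are not supported. A reader might conclude that 20 people are enough if true detection is 98–99%; the chance of success runs from about 35% to 75% at 98% and from 45% to 95% at 99%, so no such assurance follows. A reader might also conclude that the trial's main result is compromised; the between-group comparison and its power statement are unaffected.

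**What to change.** 1. **Separate the two quantities.** Report detection with doses ingested as the denominator, taken as capsules dispensed minus returned (both available at the End of Study visit) and cross-checked against the urine riboflavin results for reported but undetected doses. State that discarded capsules would bias this downward. Report the as-prescribed share of scheduled doses separately, as adherence.
2. **Give detection an interval and a rule.** Specify a two-sided 95% confidence interval with participants as clusters, for example logit-scale or beta-binomial with a small-sample correction. Include a stated rule for 100% detection. Claim more than 95% only if the lower limit exceeds 95%. Do not treat the 560–600 doses as independent.
3. **State what 20 people can support.** Say that the chance of success depends on an unknown within-person correlation. Under assumed ICC 0.02–0.20 and 600 doses it is roughly 35–75% at a true 98% and 45–95% at a true 99%, or about 61–95% at 99% if complete detection is scored as success.

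The cost is SAP wording and one additional analysis of data already being collected, with no extra participants or visits. The downside is that the bar becomes harder to meet, and a device that detects well may still fail to clear it with 20 people.

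### Hypothesis 1a claims detection of over 95% of ingestions but measures on-time recorded adherence, so a value at or below 95% cannot show whether detection exceeds 95%

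*Combined protocol and SAP*

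**What the plan says.** All references are to the combined protocol and SAP.

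- **Hypothesis 1a** states that the system will "detect over 95% of medication ingestion events as ascertained by doses of medication recorded by the ID-Cap System that are taken as prescribed". The qualification that follows ends "on time with use of ID-Cap System as instructed) over those scheduled". The claim concerns ingestion events; the denominator is scheduled doses.
- **Group Assignment/Intervention** measures Group 2 (n=20) with an "e-Tect reader worn around the neck on a lanyard". A reminder goes out if no signal arrives "within one hour of the end of the scheduled medication administration time window". If a dose is undetected but the participant reports taking it, "they will be asked to come in to the clinic to provide a urine sample for riboflavin assessment". This section also states: "Group 2 will also provide biometric data for compliance measurement, specifically ECG".
- **Study visits** plans an observed dose at randomization, a 30-day supply, and return of unused capsules at the end-of-study visit. It states no count of the returned capsules.
- **Statistical Methods, Aim 1** compares adherent days between groups by ANOVA, with a further daily binary GEE model. It gives no estimate, interval or test for Hypothesis 1a.
- **Other Statistical Considerations** treats missing compliance data as non-adherence in the primary method and promises sensitivity analyses with other methods. It does not say whether either applies to Hypothesis 1a.

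No section says whether the urine result, the returned capsules, the observed dose or the reader ECG enters the 1a ratio.

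**The concern.** Four different events lower the ratio equally: a skipped dose, a late dose, a dose taken without the reader used as instructed, and an ingested dose that the system failed to detect. Only the last is a detection failure. The reminder adds to the problem. It is sent after the dosing window has closed, so a dose that it prompts is likely to count as late even if the device records it correctly.

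At stake is the monitoring half of Aim 1. Followed as written, the plan could report participants' behaviour as a failure of the device.

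**Working it through.** **The plan's figure.** The only stated figure is the 95% target. It comes with no derivation or precision calculation, so there is nothing to reproduce.

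**Inputs.** Group 2 has 20 participants (Group Assignment/Intervention). Scheduled doses are 20 × 30 = 600 (30-day supply, Study visits; 30-day period, section 5.1) or 20 × 28 = 560 (four weeks, Overview).

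**1. What the ratio bounds.** Let T be recorded doses that were on time and as instructed, N all detected doses, I ingested doses and S scheduled doses. The 1a ratio is R = T/S; detection is N/I. With no false detections, T ≤ N. If ingested doses do not exceed scheduled doses, I ≤ S. Hence T/S ≤ N/I, and R is a lower bound on detection.

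**2. Why a value at or below 95% does not decide.** Take R = 540/600 = 90%. Detection among doses ingested on time and as instructed depends on how many such doses there were:

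| Ingested on time, as instructed | Detection of those doses |
|---|---|
| 540 | 540/540 = 100% |
| 560 | 540/560 = 96.4% |
| 580 | 540/580 = 93.1% |
| 600 | 540/600 = 90.0% |

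The same result fits detection on either side of the target.

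**3. When a perfect detector fails.** Over 95% of 600 means more than 570, so at least 571, which allows 29 shortfalls. Over 95% of 560 means more than 532, so at least 533, which allows 27. A perfect detector therefore fails at 30/20 = 1.5 missed, late or no-reader doses per participant over 30 days, or 28/20 = 1.4 over 28 days. Put another way, if 97% of scheduled doses are taken on time and as instructed, detection of those doses must exceed 0.95/0.97 = 97.9%. At 95% or less, the target cannot be met.

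**4. Missing data.** If missing counts as non-adherent for 1a, one participant of 20 with no recorded dose leaves at most 19 × 30 = 570 of 600, or 19 × 28 = 532 of 560. Both are exactly 95.0%, which is not over 95%. If that participant's first dose was recorded, 571/600 = 95.2% passes only with no other shortfall.

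**5. Illustration with assumed counts.** Of 600 capsules dispensed, 30 are returned, 10 discarded and 560 ingested. Of the ingested doses, 549 are detected, 510 of them on time. Of the 11 undetected doses, 4 were taken without the reader and 6 are riboflavin-confirmed.

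- 1a ratio: 510/600 = 85.0%, a failure.
- True detection: 549/560 = 98.0%; with the reader used, 549/556 = 98.7%.
- Riboflavin-confirmed estimate: 549/(549 + 6) = 98.9%. The Wilson 95% CI is 97.7 to 99.5 if doses are independent. At an assumed within-person correlation of 0.1 it is 95.7 to 99.7 (design effect 1 + (555/20 − 1) × 0.1 = 3.7).
- Capsule-count estimate: 549/(600 − 30) = 96.3%. The CI is 94.4 to 97.6 if independent, and 92.0 to 98.3 at 0.1 (design effect 1 + (570/20 − 1) × 0.1 = 3.75).

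**The case against.** The strongest reply is that the ratio is conservative. Under the two conditions in step 1, 94% implies detection of at least 94%, and a value above 95% is genuine support for the hypothesis. That stands. A reader might infer that a value at or below 95% carries no information about detection. This is too strong: it still bounds detection from below and only leaves open whether the target is met.

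A reader might also infer a false success from the differing periods. For example, 28 on-time detections over 28 scheduled days read 100%, while 28 of 30 ingested capsules is 93.3%. That gap arises only from changing the period between the two figures, and nothing in the documents does this for Hypothesis 1a. With one capsule a day and the same days in numerator and denominator, ingested doses exceed scheduled doses only through extra dosing, which the documents do not suggest.

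Three further replies stand in part:

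- The planned missing-data sensitivity analyses mean that the case in step 4 need not be the only result shown.
- The riboflavin check, which Design Considerations supports as a comparison marker, already collects data that help to separate non-ingestion from non-detection. It lacks a stated role in 1a.
- The GEE model could give an interval for Group 2's on-time proportion, but not for detection.

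Finally, section 5.9 calls the study preliminary, and healthy volunteers may adhere well. The documents give no expected rate for on-time dosing or reader use, so neither frequent nor rare failure can be claimed.

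**Conclusion.** The point holds and should be fixed. Hypothesis 1a states a detection claim and tests it with an adherence ratio, and no other section repairs this. The consequence is a possible false failure: with perfect detection, 5% of scheduled doses missed, late or taken without the reader is enough. This rests on the absence of false detections, which the documents do not address, and on ingested doses not exceeding scheduled ones. The single-participant result also assumes that the missing-as-non-adherent rule governs 1a.

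A reader might infer that the trial's main result is compromised. It is not: the primary outcome and the between-group comparison concern adherent days and do not depend on the 1a ratio.

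Two neighbouring inconsistencies must be reconciled but are separate points. The timing of a dose is worded differently in Hypothesis 1b ("defined as within the scheduled administration time"), Group Assignment/Intervention, Study visits and Statistical Methods. The outcome period is given in the Overview as a "proportion of days adherent to taking medication over a four week period" and in section 5.1 as 30 days.

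**What to change.** 1. Rename the present ratio 'on-time recorded adherence' and state which missing-data rule applies to it. Do not conclude from a value at or below 95% that detection failed.
2. Define detection for 1a as ID-Cap detections at any hour over doses with evidence of ingestion, using the same dose period above and below the line. Name in advance the one estimate that decides the target, and say whether its point value or its lower confidence limit must exceed 95%. One choice is detections / (detections + undetected doses reported as taken and not contradicted by the planned riboflavin urine), with a participant-clustered 95% CI. In the illustration this lies between 549/555 = 98.9% (only the 6 confirmed doses counted) and 549/560 = 98.0% (all 11 counted), if there are no false reports.
3. Show two sensitivity estimates: the version limited to riboflavin-confirmed doses, and detections over dispensed minus returned capsules. Neither is a strict bound.
4. Where the data allow, show doses taken without the reader used as instructed separately. The reader ECG could help if it is time-stamped, which the documents do not state.

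**Cost.** SAP wording, a short extra analysis and a recorded count of returned capsules.

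**Downsides.** The reference data are imperfect:

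- Riboflavin depends on self-report and attendance, and the Compensation section itself foresees missed urine visits. An adjacent day's capsule could appear to confirm a missed dose and push the estimate down; unconfirmed undetected doses push the confirmed version up.
- Discarded capsules count as ingested. With 3% discarded, 98% true detection reads 0.98 × 0.97 = 95.1%; with 5% discarded, a perfect device reads 95.0%.
- False detections remain unchecked, reader use may not be recoverable for every dose, and the interval may be wide.
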